3. ENDPOINTS

3.1 Primary efficacy endpoints

The primary efficacy endpoint for analysis is the change from baseline in HbA1c at Week 26 of the ST period. Analysis of HbA1c will be performed only in conventional (US) units (%).

HbA1c will be assessed at the time points shown in the Appendix (Section 8.1), and at non-treatment / unscheduled visits (if applicable), based on a single central laboratory test at each time point. For the primary analysis, missing HbA1c at Week 26 will be imputed based on multiple imputation (as described in Section 4.1.12).

3.2 Secondary efficacy endpoints

The secondary efficacy endpoints are:

- Change from baseline in FPG at Week 26.

Central laboratory measurements of FPG will be used for the analysis and will be restricted to measurements obtained in the fasting state. Fasting plasma glucose will be assessed at the time points shown in Appendix (Section 8.1) and at non-treatment / unscheduled visits (if applicable), based on a single central laboratory test at each time point. For secondary analyses, multiple imputation will be used to impute missing FPG values for Week 26 (as described in Section 4.1.12).

- Percentage of subjects with baseline HbA1c $\geq 7\%$ who achieve a HbA1c level $< 7\%$ at Week 26.

3.3 Exploratory efficacy endpoints

The following exploratory efficacy endpoints are defined for the study:

3.3.1 Exploratory efficacy endpoints for short term assessment of dapagliflozin and saxagliptin

- Percentage of subjects who require glycaemic rescue medication or discontinue the study medication due to lack of efficacy during the 26-week treatment period.
- Time to initiation of glycaemic rescue medication or discontinuation of study medication due to lack of efficacy during the 26-week treatment period.

3.3.2 Exploratory efficacy endpoints for short term plus long-term assessment of dapagliflozin and saxagliptin

- Change from baseline in HbA1c at Week 52.
- Change from baseline in FPG at Week 52.
- Percentage of subjects with baseline HbA1c $\geq 7\%$ who achieve a HbA1c level $< 7\%$ at Week 52.
- Time to initiation of glycaemic rescue medication or discontinuation of study medication due to lack of efficacy during the 52-week treatment period.

3.3.3 Exploratory efficacy endpoints for monotherapy assessment of dapagliflozin and saxagliptin

- Change from withdrawal baseline in HbA1c during the randomised withdrawal period.
- Change from withdrawal baseline in FPG during the randomised withdrawal period.
- Percentage of subjects who achieve or maintain an HbA1c level $< 7\%$ at the end of the randomised withdrawal period.
- Time to initiation of glycaemic rescue medication or discontinuation of study medication due to lack of efficacy using the start time of randomised withdrawal period as the reference point.

3.4 Safety endpoints

The assessment of safety will be based on the analyses of the incidence of AEs, SAEs, adverse events of special interest (AEOSI), hypoglycaemic events, discontinuations due to AEs, marked abnormalities in clinical laboratory tests, vital signs, Tanner staging, measures of growth and maturation, DKA events, and safety laboratory tests.

3.4.1 Adverse events

AEs (serious and non-serious, excluding hypoglycaemic or DKA events that are not reported as SAEs) will be collected throughout the study up to Week 56, and will also be collected quarterly between Week 56 and Week 104 via phone assessment. Adverse events will be classified by system organ class (SOC) and preferred term (PT) according to the Medical Dictionary for Regulatory Activities (MedDRA), based on the MedDRA version current at the time of database lock. Each subject will be counted once within a SOC or PT in AE frequency tables, under the maximum intensity within each category. For summaries of AEs by relationship to study drug, as assessed by the investigator (related, not related), subjects will be counted under the most

related instance within each SOC or PT. For the summary of AEs that occurred in $\geq 5\%$ of the subjects within a treatment group (based on PTs) the number of AEs will also be presented.

Events will be considered treatment-emergent if:

- The event started on or after the first dose of IP (Day 1) and up to and including 4 days for AEs and 30 days for SAEs after the last dose date.
- The event started before Day 1 but increased in intensity or relatedness to study medication on or after Day 1.
- The event onset date is missing or partial (unless the stop date of the event indicates that the event cannot be treatment emergent).
- Events will be considered treatment emergent unless they can be proven not to be so from the data.

Details for handling of missing and partial event dates for determining treatment emergence are provided in the Appendix (Section 8.2).

Listings will include the AE duration, calculated as AE stop date - AE start date + 1. AE duration will be calculated only when complete dates (at least day, month, year) for the start and stop date are provided. Each AE will be graded for intensity (mild, moderate, severe). If intensity is missing, the event will be regarded as severe. Each AE will also be assessed for relationship to the study drug (related, not related). Adverse events with missing relationship to study drug will be considered treatment-related for the purpose of summarising AEs related to study drug. Adverse events with missing flag indicating serious will be considered serious for AE summaries.

Any treatment for AEs will be reported under prior and concomitant medications (excluding rescue medication which will be reported separately). The AE number will be recorded to the corresponding medication for cross-linking purposes.

Adverse events of special interest

Adverse events of special interest will be selected by MedDRA PT and include, but are not limited to: amputations/peripheral revascularisations; changes in growth; drug-induced liver injury/marked hepatic laboratory abnormalities (including liver function test abnormalities accompanied by jaundice or hyperbilirubinemia); hypersensitivity reactions (including anaphylaxis, angioedema, exfoliative skin conditions); severe cutaneous adverse reactions (including bullous pemphigoid); genital mycotic infections; necrotising fasciitis of the perineum (Fournier's gangrene); urinary tract infections (including urosepsis/pyelonephritis); opportunistic infections; decreased lymphocyte and/or thrombocyte counts; oral soft tissue conditions (e.g., stomatitis); pancreatitis; cardiac failure (including hospitalisation for heart failure); acute kidney injury, renal impairment and/or renal failure; volume depletion; bone fractures; hyperlipidaemia; hypoglycaemic events; hyperglycaemic events; ketoacidosis; malignancies (including bladder cancer); and arthralgia.

Adverse events of special interest will be programmatically identified based on a predefined list of PTs.

Amputations and underlying conditions relevant to amputation will be recorded on a specific CRF page. The AE leading to amputation should be recorded in the eCRF as an AE/SAE. Events potentially placing the subject at risk for a lower limb amputation (“preceding events”) should also be recorded in the eCRF as an AE/SAE whether or not an amputation has taken place.

A final review will take place prior to database lock to ensure new terms not already included in the older MedDRA version are captured within the categories for the new higher MedDRA version. The list will be provided by AZ prior to Week 56 database lock.

Hepatic adverse events

A list of PTs will be selected before Week 56 database lock of the study to facilitate identification of events of hepatic disorders.

Incidence rate (exposure-adjusted)

Where specified, event summaries may include the exposure adjusted incidence rate. The incidence rate will be expressed per 100 patient-years. This is calculated as:

$$\text{Incidence rate} = 100 * \frac{n \text{ subjects with } \geq 1 \text{ event of interest}}{\text{sum}[\min(\text{exposure time}, \text{time to event})]}$$

The sum of min(exposure time, time to event) will be computed by summing up the minimum of exposure time or time to event per subject across all subjects for each treatment and dose as treated (defined in Section 2.1).

For analyses using first treatment as treated (total dapagliflozin, total saxagliptin, placebo), exposure time and time to event are defined as:

Exposure time (years) per subject is computed as (last date of exposure for that subject - date of first dose in the study + 1)/365.25. Time to event (years) for subjects having the event is computed as (date of onset of event – date of first dose in the study +1)/365.25.

For analyses using dose at onset of AE to account for the change in treatment and dose at the 2nd and 3rd randomisations, exposure time and time to event are defined as:

Exposure time (years) per subject for each treatment and dose as treated is computed as (last date of exposure to treatment and dose for that subject - date of first exposure to treatment and dose + 1)/365.25. Time to event (years) for subjects having the event whilst on the current treatment and dose is computed as (date of onset of event – date of first exposure to treatment and dose +1)/365.25.

For incidence rate analyses for events prior to rescue, if no event occurred prior to rescue medication initiation then the date of rescue medication initiation is used instead of last date of exposure.

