6.8.1 Adverse Events of Interest

The following are possible safety concerns associated with DPP-4 inhibitors and/or SGLT-2 inhibitors, which should be considered adverse events of interest and must be captured when spontaneously reported: amputations/peripheral revascularizations, changes in growth; drug-induced liver injury/marked hepatic laboratory abnormalities (including liver function test abnormalities accompanied by jaundice or hyperbilirubinemia); hypersensitivity reactions (including anaphylaxis, angioedema, exfoliative skin conditions); severe cutaneous adverse reactions (including bullous pemphigoid); genital mycotic infections; necrotizing fasciitis of the perineum (Fournier's gangrene); urinary tract infections (including urosepsis/pyelonephritis);

opportunistic infections; decreased lymphocyte and/or thrombocyte counts; oral soft tissue conditions (e.g., stomatitis); pancreatitis; cardiac failure (including hospitalization for heart failure); acute kidney injury, renal impairment and/or renal failure; volume depletion; bone fractures; hyperlipidemia; hypoglycemic events; hyperglycemic events; ketoacidosis; malignancies (including bladder cancer); and arthralgia.

For the purposes of regulatory reporting, based on whether AEs in the above categories meet the criteria for serious or nonserious AEs, they will be collected and reported according to the appropriate guidelines, as described above in Sections 6.1.1 and 6.2.1, respectively.

To ensure that data on amputations are systematically collected, amputations and underlying conditions relevant to amputation will be recorded on a specific eCRF page. The AE leading to amputation should be recorded in the eCRF as AE/SAE. Events potentially placing the subject at risk for a lower limb amputation ("preceding events") should also be recorded in the eCRF as AE/SAE whether or not an amputation has taken place. These will be collected on a dedicated eCRF page.

After the initial AE report, the Investigator is required to proactively follow each subject at subsequent visits/contacts. All AEs of interest will be followed until resolution, stabilization, the event is otherwise explained, or the subject is lost to follow-up.

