3.4.3 Other safety events

3.4.3.1 Diabetic ketoacidosis

A DKA event will not be reported on an AE CRF page unless the event fulfilled SAE criteria, in which case it should also be reported in the SAE form. Separate pages to capture details of DKA events are contained within the CRF. Details include signs and symptoms, contributing factors, whether local labs were performed, and whether the event is classified as an SAE. Adjudication findings (definite DKA, probable DKA, possible DKA, not DKA) will also be provided for DKA events sent to the Adjudication committee.

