3.4.3.2 Hypoglycaemia

Hypoglycaemia event will not be reported on an AE CRF page unless the event fulfilled SAE criteria, in which case it should also be reported in the SAE form. Hypoglycaemic events that meet SAE criteria will be recorded as SAEs by the Investigator in the AE CRF pages. Separate pages to capture details of hypoglycaemia events are contained within the CRF. Details include symptoms, contributing factors, blood glucose measurements during the episode, date and time of last meal, third party intervention, any treatment(s) received, and whether the episode is classified as an SAE. Any self-monitored blood glucose (SMBG) measurements taken by the subjects on the days that they experience hypoglycaemia symptoms will be recorded in the CRF.

Hypoglycaemia episodes will be classified using ADA¹ and International Society of Paediatric and Adolescent Diabetes (ISPAD)² categories. Derivation details based on the information collected in the separate CRF pages for hypoglycaemia are provided in the Appendix (Section 8.9).

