4.7.1.4 Adverse events leading to discontinuation of study medication

Adverse events with an onset during treatment for which the action taken was "drug permanently discontinued" will be summarised by SOC, PT, and treatment group for both the primary (including data regardless of rescue medication initiation) and sensitivity safety analyses (excluding data after rescue). This summary will include all hypoglycaemia events and all DKA events that are reported as SAEs and will be presented for the ST, ST+LT and randomised withdrawal periods. Note that, when summarising AEs leading to discontinuation, no upper cut-off day windows (i.e., 4 days and 30 days from last dosing date for AEs and SAEs respectively) will be applied. For ST period analyses, the only upper cut-off date will be the start date of the LT period.

A subject listing of discontinuation of study medication due to AEs will be provided for the ST+LT period.

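### The AEOSI rows for hypoglycaemia and ketoacidosis can hold only serious events, and the AEOSI text does not say so; the site instructions and the discontinuation summary share the gap

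*SAP*

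**What the plan says.** SAP 3.4.1 ends its AEOSI list with "hypoglycaemic events; hyperglycaemic events; ketoacidosis; malignancies (including bladder cancer); and arthralgia" and gives one way of finding every category: "Adverse events of special interest will be programmatically identified based on a predefined list of PTs". The AEOSI paragraph of SAP 4.7.1.1 then plans counts and percentages by preferred term (PT), exposure-adjusted rates for the ST+LT period, and a glossary that flags any searched term not found in the study.

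The recording rules for two of these categories differ from the rest. SAP 3.4.1 defines the AE data as "AEs (serious and non-serious, excluding hypoglycaemic or DKA events that are not reported as SAEs) will be collected throughout the study up to Week 56". SAP 3.4.3.1 says "A DKA event will not be reported on an AE CRF page unless the event fulfilled SAE criteria", and SAP 3.4.3.2 says "Hypoglycaemia event will not be reported on an AE CRF page unless the event fulfilled SAE criteria". Both kinds of event have their own CRF pages. Protocol 5.3.1.2 and 5.3.2 give sites the same rule.

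Protocol 6.8.1 lists hypoglycaemic events and ketoacidosis among the safety concerns "which should be considered adverse events of interest and must be captured when spontaneously reported". It sends non-serious ones to Section 6.2.1, which requires the non-serious AE page.

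On stopping study drug, SAP 4.7.1.4 selects AEs by the action taken and adds: "This summary will include all hypoglycaemia events and all DKA events that are reported as SAEs".

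**The concern.** The PT rule needs an AE record to search. For non-serious hypoglycaemia and DKA, the plan's own collection rule means that no such record should exist. The method named for these two categories therefore cannot deliver the categories as named.

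Three things follow:

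- The AEOSI table and its rates would read as the totals for these risks although they cover SAEs only.
- The glossary could flag hypoglycaemia terms as absent from the study while the ADA and ISPAD tables in the same report show events.
- If some sites follow Protocol 6.8.1 and others follow 5.3.1.2 and 5.3.2, the AEOSI counts would depend on site practice.

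The discontinuation table has the same weakness. Protocol 3.7.3 names recurrent hypoglycaemia as a possible reason to stop study drug, but Protocol 5.3.1.2 keeps such a stop off the AE page unless the event is serious.

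**Working it through.** The plan states no figure on this point, so there is none to reproduce. The first check is a side-by-side reading.

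| Item | Source it draws on | Non-serious hypoglycaemia or DKA included? |
|---|---|---|
| AEOSI table and rates (SAP 3.4.1, 4.7.1.1) | AE data, by PT | No; the AEOSI text is silent |
| Any-AEOSI row in the overall AE summary (SAP 4.7.1.1) | AE data | No; the lead-in to that summary says so |
| Hypoglycaemia rows in the same summary | Hypoglycaemia data | Yes: one row for any hypoglycaemia event and one for any AE or hypoglycaemia event |
| Hypoglycaemia tables (SAP 4.7.2.4) | Hypoglycaemia CRF | Yes, by ADA and ISPAD category |
| DKA tables (SAP 4.7.2.2) | Suspected DKA sent for adjudication | Yes, by adjudication category |
| AEs leading to discontinuation (SAP 4.7.1.4) | AE action taken | No |
| Events leading to discontinuation, own section | SAP 4.7.2.2 for DKA; none in 4.7.2.4 | DKA yes; hypoglycaemia has no such summary |

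The sentence in SAP 4.7.1.4 could be read as admitting every hypoglycaemia event and limiting only DKA to SAEs. Even so, the table selects on an AE field. A non-serious episode has no AE record, and the hypoglycaemia page contents listed in SAP 3.4.3.2 do not include action taken with study drug.

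SAP 4.7.2.2 plans proportions, so I find no exposure-adjusted rate that includes non-serious ketoacidosis.

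**Size of the shortfall in one AEOSI category.** Let s be the share of episodes that are serious and k the episodes per affected child. Both are assumptions, since the documents give neither. If episodes are independent, the share of affected children who appear in the AEOSI table is 1 − (1 − s)^k.

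| s | k = 1 | k = 3 |
|---|---|---|
| 2% | 2% | 1 − 0.98³ = 5.9% |
| 10% | 10% | 1 − 0.90³ = 27.1% |
| 50% | 50% | 1 − 0.50³ = 87.5% |
| 90% | 90% | 1 − 0.10³ = 99.9% |
| 100% | 100% | 100% |

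For example, take 81 children per arm (the planned number), an assumed 30% with any episode, and one episode each. Then 81 × 0.30 = 24.3 children are affected. The table shows 24.3 × 0.02 = 0.5 of them at a 2% serious share and 24.3 × 0.90 = 21.9 at 90%.

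**Size in the any-AEOSI row.** Let o be the share of children with some other AEOSI and h the share with hypoglycaemia, independent of each other. At the extreme where no hypoglycaemia is serious, the row omits (1 − o) × h. With o = 20% in both arms and h = 20% on placebo and 30% on drug:

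- All events counted: 1 − 0.8 × 0.8 = 36% on placebo and 1 − 0.8 × 0.7 = 44% on drug.
- As written: 20% in both arms, which is 16 and 24 points lower, so an 8-point difference is missing from that row.
- Over o from 10% to 30%, and h from 10–20% on placebo against 15–30% on drug, the row is 7 points (0.7 × 0.10) to 27 points (0.9 × 0.30) lower. The difference missing from it is 3.5 points (0.7 × 0.05) to 9 points (0.9 × 0.10).

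If every episode were serious, both quantities would be zero.

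**The case against.** The strongest reply is that separate analysis is the declared design. SAP 3.4 lists AEOSI, hypoglycaemic events and DKA events as distinct safety endpoints. SAP 3.4.1 and the lead-in to the overall summary in 4.7.1.1 both state the exclusion of non-serious events, and SAP Table 12 declares that 4.7.1.1 presents only adjudicated DKA SAEs. AE rates are not formally tested. Two tables with different stated scopes do not contradict each other.

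Much of this stands. A reader might infer that a drug–placebo difference in hypoglycaemia disappears from the report. It does not: the summary that holds the any-AEOSI row also has a row for any hypoglycaemia event, and SAP 4.7.2.4 tabulates the full data. A reader might also infer that the AEOSI rates are far too low. That needs a low serious share, which the documents do not give and which may differ between hypoglycaemia and DKA.

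Merging the sources has its own cost. The primary hypoglycaemia analysis stops at first rescue (SAP Table 8, 4.7.2.4), whereas the primary AE analyses run regardless of rescue. The hypoglycaemia data also include asymptomatic glucose values of 70 mg/dl or less (SAP Table 20), which could dominate an any-AEOSI row. On discontinuation, SAP 4.2.1 does tabulate treatment discontinuations by reason.

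The reply does not cover the AEOSI paragraphs themselves, the glossary flag, the conflict between Protocol sections, or the missing hypoglycaemia counterpart to the DKA discontinuation summary. Protocol 5.3.1.2 and 5.3.2 can be read as the specific rule that overrides the general one in 6.8.1, but 6.8.1 makes no such exception.

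**Conclusion.** The point holds as a mismatch between source and label, not as a loss of safety data. As specified, the AEOSI table, its rates and the any-AEOSI row are restricted to SAEs for hypoglycaemia and ketoacidosis, and the AEOSI text does not say so. The shortfall runs from almost total to none, depending on a serious share that the documents do not supply. The percentages shown in the working are illustrations on assumed inputs, not estimates for this trial. The full data remain reported in SAP 4.7.1.1, 4.7.2.2 and 4.7.2.4, and no formal inference is affected.

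Two related defects rest on the text alone. Protocol 6.8.1 read with 6.2.1 contradicts 5.3.1.2 and 5.3.2 on the recording page. Stopping study drug for non-serious hypoglycaemia falls outside the AE-discontinuation table and has no summary of its own. These should be corrected because the stated rule cannot produce the categories it names and the correction is cheap.

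**What to change.** 1. In SAP 3.4.1 and 4.7.1.1, choose one of two routes.
   - Derive the hypoglycaemia category from the hypoglycaemia CRF and the ketoacidosis category from the adjudicated DKA data, count both in the any-AEOSI row, and state that they are counted regardless of rescue like the other AEs.
   - Or keep the PT rule and label the two categories *SAEs only; see 4.7.2.2 and 4.7.2.4* in the tables, the rates and the PT glossary.
2. Add to SAP 4.7.2.4 a summary of study-drug discontinuation due to hypoglycaemia, serious or not. If the hypoglycaemia page has no action-taken field, use the recorded reason for treatment discontinuation, which Protocol 3.7 requires.
3. Reconcile Protocol 6.8.1 with 5.3.1.2 and 5.3.2 on where non-serious events of these two kinds are recorded.

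The labelling route costs a few footnotes. The derivation route costs programming on data already planned for collection, and the any-AEOSI percentages can only stay the same or rise. The discontinuation summary depends on whether the recorded reason identifies hypoglycaemia; the documents do not show this, so check the CRF first.

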If a subject discontinues IP early (prior to the Week 52 visit), at the next visit the subject should be assessed according to the follow-up schedule for Early Treatment Discontinuation (ETD) (Table 5.1-4). The reason for early discontinuation must be documented in the subject's medical records and entered on the appropriate CRF page.

Subjects who discontinue IP early will still be evaluated for rescue.

After discontinuation of IP the management of the subject's diabetes will be under the care and direction of the Investigator.

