For those data which will be listed, each subject will appear in the listings with their subject identifier, age, sex, race and background medication. Only subjects with data available will be presented in the listings. If a visit took place but no data is entered for the type of assessment being listed (other than 'Not Done'), the entry will not be listed. Subject data listings will be sorted by subject identifier, treatment group, dose (low, low/high) as per first randomisation, up-titration, and third randomisation, and if applicable, parameter group, parameter name, nominal visit name, analysis visit name (Baseline, Week 2, etc.), visit date and date/time of assessment (with corresponding day relative to first dose), unless specified otherwise. Events that occurred after first rescue medication use will be flagged in the efficacy listings.

Table 8 Cut-off dates for analyses by analysis type and study period

Data	Analysis type*	ST period ^a	ST+LT period ^a	Randomised withdrawal period ^{a,e}
Safety analyses				
AE, non-serious DKA	Prim	
 Start of LT period (if applicable) Date of last dose during the ST period + 4 days^b 	
 Week 52/ETD date + 4 days^b 	
 Week 52/ETD date + 4 days^b
	Sens	
 Start of LT period (if applicable) Date of last dose during the ST period + 4 days^b First rescue intake^d 	
 Week 52/ETD date + 4 days^b First rescue intake^d Week 32^f/ETD date + 4 days^b Week 32^f/ETD date + 4 days^b First rescue intake^d 	
 Week 52/ETD date + 4 days^b First rescue intake^d
SAE (including serious DKA, serious Hypoglycaemia)	Prim	
 Start of LT period (if applicable) Date of last dose during the ST period + 30 days^b 	
 Week 52/ETD date + 30 days^b 	
 Week 52/ETD date + 30 days^b
	Sens	
 Start of LT period (if applicable) Date of last dose during the ST period + 30 days^b First rescue intake^d 	
 Week 52/ETD date + 30 days^b First rescue intake^d Week 32^f/ETD date + 30 days^b Week 32^f/ETD date + 30 days^b First rescue intake^d 	
 Week 52/ETD date + 30 days^b First rescue intake^d

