4.3 Extent of exposure to study treatment

4.3.1 Extent of exposure to IP treatment

Extent of exposure to IP will be summarised (regardless of rescue medication initiation) using the Treated Subjects Data Set for the ST and ST+LT treatment periods, and the Randomised Withdrawal Subjects Data Set for the randomised withdrawal period. These summaries will be repeated for exposure prior to rescue medication initiation.

Extent of exposure is defined as last dose date - first dose date + 1, with the last dose date being the last dose of the concerned period. Extent of exposure (days) will be summarised by treatment group as a continuous variable as well as for pre-specified day ranges (ST period: 1-7, 8-14, 15-28, 29-42, 43-56, 57-70, 71-84, 85-98, 99-140, 141-182, > 182 days; ST+LT period: 1-90, 91-180, 181-270, 271-365, and > 365 days; randomised withdrawal period: 1-7, 8-14, 15-28, 29-42, 43-56, 57-70, 71-112, 113-154, > 154). In addition, the exposure in terms of total patient-years will be summarised by treatment group using the sum of the exposure to IP of all subjects (in years) in a treatment group.

Individual subject dosing and exposure to IP by study period will be listed.

A listing of subjects by batch number of study medication will also be generated.

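### Exposure-adjusted incidence rates stop person-time at the last dose but count SAEs for 30 days (AEs for 4) after it, and the pre-rescue rule can add off-drug days in which no event can count

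*SAP*

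**What the plan says.** **Numerator.** SAP 3.4.1 treats events as treatment-emergent "up to and including 4 days for AEs and 30 days for SAEs after the last dose date". Table 8 (SAP 4.1.7) applies the same windows by period. For SAEs the ST+LT and randomised withdrawal cut-off is "Week 52/ETD date + 30 days". The ST cut-off is the earlier of the start of the LT period and "Date of last dose during the ST period + 30 days". Footnote a of Table 8 says that the earliest date governs where several are listed.

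**Denominator.** SAP 3.4.1: "The sum of min(exposure time, time to event) will be computed by summing up the minimum of exposure time or time to event". For the analyses by first treatment, exposure time is ("last date of exposure for that subject - date of first dose in the study + 1)/365.25". No 4-day or 30-day extension is added. SAP 4.3.1 agrees that exposure stops at the last dose: "Extent of exposure is defined as last dose date - first dose date + 1".

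**Pre-rescue version.** If a subject had no event before rescue, "then the date of rescue medication initiation is used instead of last date of exposure". Nothing limits this to the earlier of the two dates. Protocol 3.7 states: "Subjects who discontinue IP early will still be evaluated for rescue". Protocol 3.7.2 lets rescue be triggered from Week 6 up to, but not including, Week 52. A rescue date can therefore fall well after the last dose.

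**Where the rates appear.** SAE rates are planned in SAP 4.7.1.3, and AE rates (including pre-rescue) in SAP 4.7.1.1.

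**The concern.** A rate is interpretable when the person-time covers the same days in which an event could be counted. Here the two do not match, in two ways.

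First, an SAE on day 20 after the last dose enters the numerator, but no subject contributes any of the 30 post-dose days. This can only push rates up, and it does so most where exposure is short.

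Second, a child who stops drug and is rescued months later contributes all the days up to rescue, although the pre-rescue numerator closes at the earliest Table 8 date. This can only push pre-rescue rates down.

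Exposure adjustment is there to make event rates in these children comparable across arms and across periods of different length. At stake is whether the tabulated rates do that.

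**Working it through.** The plan states no incidence rate, expected event count, discontinuation rate or rescue rate, so there is no figure of its own to reproduce. Hazards, stopping shares and stopping times below are assumptions.

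**1. Post-dose window.** Let T be days from first to last dose, w the window (4 or 30) and L a constant hazard.

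- Expected counted events per child: 1 − exp(−L(T + w)).
- SAP person-time per child: (1 − exp(−LT))/L.
- For rare events the rate is therefore too high by a factor of about (T + w)/T.

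| Last dose (day) | SAEs, w = 30 | AEs, w = 4 |
|---|---|---|
| 42 | 72/42 = 1.714 | 46/42 = 1.095 |
| 98 | 128/98 = 1.306 | 102/98 = 1.041 |
| 182 | 212/182 = 1.165 | 186/182 = 1.022 |
| 365 | 395/365 = 1.082 | 369/365 = 1.011 |

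**2. Whole arm, ST+LT, SAEs.** Assume 81 children, a true rate of 10 per 100 person-years, and everyone else treated to Day 365.

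- No early stopping: 8.303 events / 77.032 person-years = 10.78.
- 5% stop at Day 42: 7.967 / 73.643 = 10.82.
- 30% stop at Day 42: 6.286 / 56.700 = 11.09.
- 10% stop at Day 98: 7.751 / 71.473 = 10.845.
- 20% stop at Day 98: 7.200 / 65.914 = 10.923.

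Between-arm ratio when the true ratio is 1: 11.087/10.818 = 1.025 (30% v 5% at Day 42) and 10.923/10.845 = 1.007 (20% v 10% at Day 98).

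**3. ST period, SAEs.** The start of the LT period closes the window, so completers who enter LT have no tail. Taking ST person-time to end with the ST period, the rate is 10.00 with no stoppers, 10.18 if 10% stop at Day 42 and 10.65 if 30% do.

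**4. Pre-rescue rule, one child.** Last dose Day 60, rescue Day 250, no event before rescue. Counted time is 250 days. Eligible time is 60 + 4 = 64 days for AEs (250/64 = 3.9) or 60 + 30 = 90 days for SAEs (250/90 = 2.8).

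**5. Pre-rescue rule, whole arm.** Let r be the rescue day and e = min(T + w, r).

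- Expected events per child: 1 − exp(−Le).
- SAP person-time per child: (1 − exp(−Le))/L + exp(−Le)(r − e).

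Take last dose Day 42, rescue Day 182 and an assumed AE rate of 50 per 100 person-years. Such a child's expected rate is 12.94, or 0.26 of the true rate. If 5%, 10% or 20% of the arm follow that path and the rest stay on drug to Day 365 without rescue, the arm's AE rate is 49.27, 48.08 or 45.53. That is 0.985, 0.962 or 0.911 of the true rate. For SAEs at 10 per 100 person-years the two errors offset, and the net ratios are 1.06, 1.04 and 1.00.

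**6. With matched windows.** Person-time becomes (1 − exp(−Le))/L, with e the end of the event window. Dividing events by it returns L exactly, so the between-arm ratio is 1.000 in every stopping scenario.

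**The case against.** **Little rests on these rates.** SAP 4.7.1.1 plans no test of AE rates between arms. Numbers and percentages of subjects are the main display, pre-rescue AE rates are sensitivity analyses, and hypoglycaemia is tabulated as number and proportion (SAP 4.7.2.4). This stands and limits the consequence.

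**The rate is labelled exposure-adjusted, and exposure is defined consistently as first to last dose.** That is a coherent choice only if the numerator is also confined to exposure. It is not, so the mismatch remains.

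**The intent of the pre-rescue rule is truncation.** SAP 3.5.4 describes pre-rescue exposure as running up to and including the day of rescue, and Table 8 footnote a takes the earliest date. For a child rescued while on drug, the rule does correctly shorten person-time. The intent is probably as claimed, but SAP 3.4.1 as written does the opposite for a child rescued after stopping, and so conflicts with both places.

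**Stronger readings that a reader might infer:**

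- Arm-level rates wrong by the per-child factors, such as 30/56 = 54% for a child stopping at 8 weeks, or the 3.9 above. These describe single early stoppers, and 3.9 applies to AEs only.
- A 21–36% inflation in the withdrawal period (30/140 to 30/84). SAP 3.4.1 defines no withdrawal-period denominator. Its dose-at-onset version ties time to event to events on the current treatment and dose, so the handling of post-dose events there is unclear.
- Seriously distorted between-arm comparisons. The completers' 8% applies to every arm and largely cancels, and the documents give no stopping rates that would support more.

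**Conclusion.** The concern holds as a specification error of limited size. Counting post-dose events without post-dose person-time inflates ST+LT SAE rates by about 8% for 52-week completers and by more for early stoppers. For AEs the 52-week figure is about 1%. The between-arm ratio shifts by about 1–3% in the scenarios tried.

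The pre-rescue rule affects only children who stop drug, have no earlier event and later start rescue insulin. If 5–20% of an arm took the assumed Day 42 to Day 182 path, that arm's pre-rescue AE rate would fall to about 0.99–0.91 of its true value.

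These sizes rest on a constant hazard and on assumed event rates, stopping shares and times. The directions do not. No tested conclusion is touched, but a stated rule that gives a wrong rate should be corrected.

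**What to change.** In SAP 3.4.1, end each subject's person-time at the earliest of first event, last dose + 4 days (AEs) or + 30 days (SAEs), and the applicable Table 8 cut-off. For pre-rescue rates, use the earlier of that date and first rescue intake.

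While editing, use one anchor: Table 8 counts from the Week 52/ETD date in the ST+LT and withdrawal periods, whereas SAP 3.4.1 and 4.7.1.3 count from the last dose. Also state how person-time closes for AEs leading to discontinuation, which have no upper window (Table 8 footnote b).

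The cost is two lines of text for the main change and a small program change, with no new data. SAE rates become slightly lower, and some pre-rescue rates slightly higher.
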